5.5 Prior and Concomitant Therapy

During the study, participants may not take proton pump inhibitors, local or systemic corticosteroids, or other immunomodulatory or immunosuppressive medications (anti-TNF for example). Patients may not take other anti-histamines. For symptoms of dyspepsia or abdominal discomfort, patients may take over-the-counter medications including bismuth subsalicylate, sucralfate, and calcium carbonate.

No major dietary changes will be allowed during the study period.

5.6 Packaging

Patients will pick up the study drugs at the Mayo Clinic pharmacy. Loratadine will be dispensed as 10 mg tablets, count of 84. Famotidine will be dispensed as 40 mg tablets, count of 168. This is a 12 week supply of both study medications.

Patients randomized to the placebo arm will receive placebo pills dispensed in similar shape, size, and color.

5.7 Masking/Blinding of Study

Subjects will be masked as to the treatment allocation. The study PI and co-investigator AK will be unblinded to monitor for adverse events. The study pharmacy will be unblended for the allocation of the study medications. Patients will be randomized in a 1:1 fashion to the two study arms using a blocked randomization protocol with a computer generate program.

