For this study, the study treatment follow-up period is defined as from the initiation of the study drugs or placebo until the 12 week follow-up appointment.

Preexisting Condition

A preexisting condition is one that is present at the start of the study. A preexisting condition should be recorded as an adverse event if the frequency, intensity, or the character of the condition worsens during the study period.

General Physical Examination Findings

At screening, any clinically significant abnormality should be recorded as a preexisting condition. At the end of the study, any new clinically significant findings/abnormalities that meet the definition of an adverse event must also be recorded and documented as an adverse event.

Post-study Adverse Event

All unresolved adverse events should be followed by the sponsor-investigator until the events are resolved, the subject is lost to follow-up, or the adverse event is otherwise explained. At the last scheduled visit, the sponsor-investigator should instruct each subject to report, to the sponsor-investigator, any subsequent event(s) that the subject, or the subject's personal physician, believes might reasonably be related to participation in this study.

Abnormal Laboratory Values

A clinical laboratory abnormality should be documented as an adverse event if they are considered clinically significant or require therapy.

Hospitalization, Prolonged Hospitalization or Surgery

Any adverse event that results in hospitalization or prolonged hospitalization should be documented and reported as a serious adverse event unless specifically instructed otherwise in this protocol. Any condition responsible for surgery should be documented as an adverse event if the condition meets the criteria for an adverse event.

Neither the condition, hospitalization, prolonged hospitalization, nor surgery are reported as an adverse event in the following circumstances:

• Hospitalization or prolonged hospitalization for diagnostic or elective surgical procedures for a preexisting condition. Surgery should not be reported as an outcome of an adverse event if the purpose of the surgery was elective or diagnostic and the outcome was uneventful.

• Hospitalization or prolonged hospitalization required to allow efficacy measurement for the study.

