8.2 Recording of Adverse Events

At each contact with the subject, the study team must seek information on adverse events by specific questioning and, as appropriate, by examination. Information on all adverse events should be recorded immediately in the source document, and also in the appropriate adverse event section of the event tracking log (see attached form). All clearly related signs, symptoms, and abnormal diagnostic, laboratory or procedure results should recorded in the source document.

All adverse events occurring during the study period must be recorded. The clinical course of each event should be followed until resolution, stabilization, or until it has been ultimately determined that the study treatment or participation is not the probable cause. Serious adverse events that are still ongoing at the end of the study period must be followed up, to determine the final outcome. Any serious adverse event that occurs during the Adverse Event Reporting Period and is considered to be at least possibly related to the study treatment or study participation should be recorded and reported immediately.

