8.4 Unmasking/Unblinding Procedures

The PI and co-investigator AK will be unblinded to monitor for adverse events. In the circumstance that an event occurs which may require unbinding of a study participant, the study team including the PI will meet and discuss the event. Unblinding will be reported in a timely manner using the same requirements for the reporting of serious adverse events.

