8.6 Medical Monitoring

It is the responsibility of the Principal Investigator to oversee the safety of the study. This safety monitoring will include careful assessment and appropriate reporting of adverse events as noted above, as well as the construction and implementation of a site data and safety-monitoring plan (see section 10 "Study Monitoring, Auditing, and Inspecting"). Medical monitoring will include a regular assessment of the number and type of serious adverse events.

9 Data Handling and Record Keeping

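### The PI and one co-investigator know treatment throughout, while the PI helps judge what counts as an adverse event, a primary outcome; no available text keeps either of them out of those judgements

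*Combined protocol and SAP*

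**What the plan says.** On masking, section 5.7 says "Subjects will be masked as to the treatment allocation" and names no other masked party. The PI and one co-investigator "will be unblinded to monitor for adverse events", and section 8.4 repeats this. The pharmacy is also unblinded, in order to allocate the medication. Section 8.4 goes on to say that, for an event that may call for unblinding a participant, "the study team including the PI will meet and discuss the event".

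On safety, the Study Summary and section 3.4 make it a primary outcome beside the eosinophil count. Section 8.3 has the sponsor-investigator evaluate each event. Section 8.5 has the study team and the PI evaluate events, with stopping the study among the possible actions. Section 8.6 states: "It is the responsibility of the Principal Investigator to oversee the safety of the study", and includes in this "careful assessment and appropriate reporting of adverse events".

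On what is counted, section 8.2 is broad: "All adverse events occurring during the study period must be recorded". Section 8.1 adds elements of judgement. At the end of the study, "any new clinically significant findings/abnormalities that meet the definition of an adverse event must also be recorded". A laboratory abnormality is an adverse event if it is judged clinically significant or needs treatment. Seriousness rests in part on the sponsor-investigator's opinion.

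**The concern.** Someone who knows the arm can apply a different threshold in each arm without intending to. Where the outcome is a judgement, the resulting error is systematic: it does not average out as patients are added, and nothing in the data reveals it. Here the person with standing knowledge of treatment is also the person responsible for safety assessment, and safety is half of the primary objective. The same count enters the review after 25 patients in section 8.5, so a classification made with knowledge of treatment could also bear on whether enrolment continues.

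**Working it through.** No figure in the plan depends on the masking arrangement, so the check is mainly a comparison of sections.

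**1. Is the unblinding conditional?** No. Sections 5.7 and 8.4 both state it without an event, a time or a request that would trigger it.

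**2. Do the unblinded people assess safety?** The PI does: sections 8.5 and 8.6 name the PI directly. Section 8.3 names the sponsor-investigator. The documents treat the two as one person only by implication, but the point does not depend on that. For the co-investigator, adverse-event monitoring is the stated reason for being unblinded.

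**3. Which parts of the safety outcome involve judgement?**

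| Element | Section | Judgement? | Assessor stated to be masked? |
|---|---|---|---|
| Recording of reported events | 3.6, 8.2 | Little; all are recorded | Not stated; the coordinator runs weeks 4 and 8 (6.2, 6.3) |
| Laboratory abnormality counted as an event | 8.1 | Yes, clinical significance | No |
| New examination finding at end of study | 8.1 | Yes, clinical significance | No; the week-12 visit is with an investigator (6.4) |
| Seriousness | 8.1 | Partly, by opinion | No |
| Withdrawal for intolerance or worsening | 4.4.1 | Yes; no decision-maker named | No |
| Withdrawal for low compliance | 5.4 | Little; pill count against 70% | Not stated |

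The exposure therefore lies in rows two to five. Nothing available excludes the two unblinded people from any of them.

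**4. What is one decision worth?** Sections 3.2 and 7.1 plan 20 patients per arm and inflate for 20% dropout: 40 / (1 − 0.20) = 50 enrolled, or 25 per arm. If k patients in one arm are classified differently, the percentage of that arm with an event shifts by 100 × k / n:

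- n = 25: k = 1 gives 4 points; k = 2 gives 8 points.
- n = 20: k = 1 gives 5 points; k = 2 gives 10 points.

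Here k is an assumption. The documents give neither the share of patients with a finding that needs judgement nor how far knowledge of treatment would change the classification, so no expected bias can be calculated.

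**5. The review after 25 patients.** Section 8.5 says the study continues if there have been no more than 2 adverse events. At a count of 2, one further finding classed as an event gives 2 + 1 = 3, which is outside the only stated condition for continuing. This shows how sensitive the count is to one classification; it is not a comment on the rule itself.

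**6. Section 8.4 read as a whole.** Its opening gives the PI the allocation at all times. The next statement has the team, PI included, discuss whether to unblind a participant. These can both hold if the second means revealing allocation to the participant or to masked staff, but the section does not say to whom.

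**The case against.** The strongest reply is that the exposed part is small and openly declared. The plan does not call itself double-blind, every adverse event must be recorded, and the coordinator handles the week-4 and week-8 contacts. That stands, and it confines the point to the judgements in rows two to five. Disclosure, however, does not remove the bias. Nor does managing an event need standing unblinding, because section 8.4 already describes case-by-case unblinding and the pharmacy already knows the allocation.

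A second reply is that the monitoring plan cited in section 10.1 as attached may assign these roles. It was not available, so this remains open; if it does, a cross-reference settles the matter.

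Several stronger readings are tempting but not supported:

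- A reader might infer that biased relatedness judgements distort the endpoint. In section 8.2, an event "considered to be at least possibly related to the study treatment or study participation" is subject to immediate recording and reporting if serious, and in section 8.1 relatedness helps define an unanticipated problem. Neither limits the safety endpoint to related events.
- A reader might infer a biased between-arm test or confidence interval for adverse events. Section 7.2 specifies neither.
- A reader might infer bias in the eosinophil count. The pathologist is not listed as unblinded. Post-treatment counts exist only after the week-12 endoscopy, so earlier removal cannot select on them. The unblinded co-investigator is not one of the two listed endoscopists; whether the PI is cannot be seen from the available text.
- A reader might infer that allocation concealment fails. List generation by the statistical team (5.2) and allocation by the pharmacy (5.7) are compatible with concealment, and section 4.3 offers enrolment to all eligible patients.
- A reader might call section 8.4 self-contradictory. It is an unresolved tension, as step 6 shows.

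**Conclusion.** The point holds in limited form. As written, the plan lets people who know the treatment decide whether laboratory and examination findings count as adverse events, whether some events are serious, and whether a patient is withdrawn. These decisions affect a primary outcome and, through the event count, the 25-patient review. The size can be stated only per decision: 4 or 5 percentage points of an arm for one patient, and one event between a count of 2 and a count of 3. That bias would occur is not shown; that the plan permits it and could avoid it cheaply is. The conclusion assumes that the unavailable monitoring plan and adverse-event form do not already assign these judgements to a masked person. It is a worthwhile improvement, not a flaw that invalidates the trial.

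**What to change.** In sections 5.7 and 8.4, replace standing unblinding with masking of the PI, co-investigators, coordinator, endoscopists and pathologist. Let the pharmacy and the statistical team that generates the list hold the code. Break it for an individual patient through the section 8.4 process, and state there to whom the allocation is revealed. Align sections 8.3, 8.5 and 8.6 so that adverse events are evaluated by masked members of the study team; changing 5.7 and 8.4 alone would leave those sections out of step.

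If a role must remain unblinded, name it, and have a masked investigator already on the team make the clinical-significance, seriousness and withdrawal judgements. If the attached monitoring plan already provides for this, cite it in 5.7 and 8.4.

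None of this alters the criteria for withdrawal or for stopping. The cost is protocol wording and a pharmacy-held code-break procedure; section 5.6 already provides a similar-looking placebo, and no new staff are needed. The downsides are a short delay when a code is broken, and minor work if safety summaries by coded arm are supplied.

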5.8 Receiving, Storage, Dispensing and Return

5.8.1 Receipt of Drug Supplies

Study participants will pick up the study medications, either treatment or placebo arm, at the Mayo Clinic pharmacy.

5.8.2 Storage

Medications (loratadine, famotidine, and/or placebo) should be stored at room temperature in a dry location and protected from light.

5.8.3 Dispensing of Study Drug

On the 12 week follow-up appointment, the treating physician will perform a pill count to document the amount of drug remaining. The pill count will be entered into the study database.

5.8.4 Return or Destruction of Study Drug

At the completion of the study, there will be a final reconciliation of drug remaining at the 12 week follow-up visit. This reconciliation will be logged into the study database. Any discrepancies noted will be documented and investigated, prior to return or destruction of unused study drug. Drug destroyed on site will be documented in the study files.

6 Study Procedures

6.1 Visit 1 (Enrollment)

Once patients have met enrollment criteria and consented to enrollment in the study, they will be given the Dysphagia Symptom Questionnaire to complete daily for two weeks. All study subjects will be given famotidine 40 mg oral twice daily and loratedine 10 mg once daily for 12 weeks or placebo pills for 12 weeks duration dispensed from the Mayo Clinic pharmacy which will be started after completing the DSQ for two weeks. Subjects will receive a diary to track medication administration and symptoms. The patient consent can performed via Zoom per patient preference.

6.2 Visit 2 (4 week follow-up after starting study drugs)

This visit will occur per participant preference, either via phone call or in person by appointment, with the study coordinator and will occur at 4 weeks plus or minus a one week period after initiation of the study drugs. Study participants will review medication compliance and adverse effects.

6.3 Visit 3 (8 week follow-up after starting study drugs)

This visit will occur per participant preference, either via phone call or in person by appointment, with the study coordinator and will occur at 8 weeks plus or minus a one week period after initiation of the study drugs. Study participants will review medication compliance and adverse effects.

6.4 Visit 4 (12 week follow-up)

At the 12 week follow-up visit with a physician, we will review the results of the DSQ to be completed for weeks 10-12 of the study drugs. The 12 week follow-up appointment will occur no earlier than 12 weeks after initiation of the study drug and no later than 14 weeks after initiation. The patient will meet with one of the study investigators, and be consented for an EGD. An EGD with esophageal biopsies will be performed. Prior to EGD, a complete blood count and basic

metabolic panel will be ordered as routine per institutional policy. Either KD or DF will perform the EGD in the endoscopy suite, per our institution's standard protocol. Any macroscopic abnormalities seen in the esophagus will be documented and photographed. Any lesions in the upper digestive tract seen on EGD will be biopsied and treated as deemed appropriate by the performing endoscopist. Biopsy specimens will be labeled and placed in a container and labeled with the patient's ID number.

The eosinophil count will be determined by the study pathologist for the post-treatment exam using a previously validated protocol. [2, 3] Four esophageal biopsies will be sampled from both the distal esophagus (3cm above the GE junction) and proximal esophagus (at least 10 cm above the GE junction) to maximize sensitivity of detecting eosinophils.[1] On each biopsy fragment, 5 high-power fields will be examined and the overall peak eosinophil count determined from the field deemed to be most inflamed from all esophageal levels and all high power fields. [4]

Symptomatic improvement will be defined as at least 2 levels on the dysphagia questionnaire.

Study Activity	Week 0 (initial enrollment appointment)	Week 6	Week 10	Weeks 14-16 (follow-up appointment)
Study Agent(s) (weeks 2-14)		X	X	
Informed consent	X			
Physician office visit with medication review and physical exam	X			X
Phone or office visit with study coordinator		X	X	
Pill count		X	X	X
Drug diary		X	X	
Adverse event evaluation		X	X	Х

B-HCG (non-menopausal females)	X		
Dysphagia Symptom Questionnaire (complete weeks 0-2 and 12-14)	X		X
CBC and BMP			X
EGD w/ biopsy			X

7 Statistical Plan

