5.1 Description

Loratadine is an oral non-sedating anti-histamine which is highly selective for H1-receptors. H1-antagonists such as loratidine compete with free histamine for binding at H1-receptor sites, which blocks the effects of histamine on H1-receptors in the GI tract through competitive antagonism. Compared to traditional sedating anti-histamines, loratadine is not associated with QT prolongation and has less central nervous system effects. Compared to first generation anti-histamines, loratadine has reduced penetration of the blood brain barrier and greater specificity for the H1 receptor with fewer anti-cholinergic effects. Loratadine is used in the pediatric and adult population for allergic rhinitis and chronic idiopathic urticaria. The standard dose is 10 mg PO once daily. After oral administration, the onset of action occurs within 1-3 hours with peak effects in 8-12 hours and duration of action greater than 24 hours.

Famotidine is an oral histamine type 2 receptor antagonist that inhibits the action of histamine at the histamine H2-receptors, including gastric cells, used for gastrointestinal disorders including gastroesophageal reflux disease and peptic ulcer disease. Oral absorption is approximately 40-45%, and the elimination half-life is 2.5-3.5 hours.

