5.2 Treatment Regimen

Famotidine will be taken 40 mg twice daily by mouth for 12 weeks. Loratadine will be taken 10 mg daily by mouth for 12 weeks.

Patients will be randomly assigned to either the treatment or placebo group by a blocked randomization protocol from a computer generated program via the Mayo Clinic statistical team.

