5.3 Preparation and Administration of Study Drug

Preparation of the study drug will be performed in the pharmacy for both famotidine and loratadine, and 12 week supplies given to the patient. Famotidine should be taken by mouth 30-60 minutes before the morning and evening meals, and Loratadine should be taken 30-60 minutes before the morning meal.

Similarly, the placebo drugs will be prepared by the pharmacist, with identical instructions for administration as the treatment drugs.

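### Drug supply ends at day 84 but the primary biopsy may be taken up to day 98, so a fully adherent patient may be 0 to 14 days off drug when it is taken

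*Combined protocol and SAP*

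**What the plan says.** **Dosing and supply.** Section 5.2 states "Loratadine will be taken 10 mg daily by mouth for 12 weeks", with famotidine 40 mg twice daily over the same period. Section 5.3 has "12 week supplies given to the patient". Section 5.6 gives the counts, 84 loratadine and 168 famotidine tablets, and adds "This is a 12 week supply of both study medications".

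**Final visit.** Section 6.4 places the follow-up appointment "no earlier than 12 weeks after initiation of the study drug and no later than 14 weeks after initiation" and describes the EGD with esophageal biopsies under that visit. In the schedule table the drug row is labelled "Study Agent(s) (weeks 2-14", and the EGD is marked in the column headed "Weeks 14-16 (follow-up appointment". The drug row has no mark in that column.

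**Symptoms.** Section 6.4 says "we will review the results of the DSQ to be completed for weeks 10-12 of the study drugs". Section 3.1 likewise ties the second DSQ period to the end of treatment and not to the biopsy date.

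**Tracking of doses.** Section 5.4 has patients keep a diary of dose times and calls for a pill count at the final visit. The schedule table marks the pill count at the final visit, but marks the drug diary only at weeks 6 and 10.

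**The concern.** The final visit can be on time or late, but never early, and the tablets run out on the first day it is allowed. For a fully adherent patient, each day of delay is a day without drug before the measurement that decides the trial. The biopsy gives the peak eosinophil count (primary endpoint, section 3.4) and the proportion at or below 15 eos/hpf, and the same EGD gives EREFS (both section 3.5).

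Patients on placebo have no drug effect to lose. If the active drugs lower eosinophils and the counts rise again after stopping, late biopsies would move the active arm toward placebo and shrink the between-arm difference. The DSQ would not be affected in the same way, because it is completed on drug. Symptom and tissue results could then differ partly because one was measured on drug and the other off it.

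**Working it through.** **1. Reproduce the stated supply (section 5.6, regimen from 5.2).**

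- Loratadine: 84 tablets / 1 per day = 84 days.
- Famotidine: 168 tablets / 2 per day = 84 days.
- 12 weeks x 7 = 84 days. The plan's figure is exact, so there is no spare supply.

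**2. Visit window (section 6.4), counting days from the first dose.**

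- Earliest: 12 x 7 = day 84. Latest: 14 x 7 = day 98.
- The schedule table agrees. Its weeks start at enrollment and drug starts at week 2, so its weeks 14-16 are 14 - 2 = 12 to 16 - 2 = 14 weeks after the first dose.

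**3. Days off drug at biopsy = EGD day - 84, full adherence.**

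| EGD | Day | Days off drug | Share of interval covered by supply |
|---|---|---|---|
| Week 12 | 84 | 0 | 84/84 = 100% |
| Proposed latest booking | 87 | 3 | 84/87 = 96.6% |
| Week 13 | 91 | 7 | 84/91 = 92.3% |
| Week 14 | 98 | 14 | 84/98 = 85.7% |

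**4. Can the gap be recovered from the data?** For a fully adherent patient, yes: EGD date minus start date minus 84. The pill count alone cannot do it, because zero tablets left looks the same at day 84 and at day 98. For a patient who missed doses, the last-dose date has to come from the diary, which the schedule does not mark at the final visit.

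**5. Supply needed to cover the whole window.**

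- Loratadine: 98 x 1 = 98 tablets, 14 more. Famotidine: 98 x 2 = 196 tablets, 28 more.
- For 50 patients: 14 x 50 = 700 and 28 x 50 = 1,400 more tablets, counting active and placebo together.

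**6. Effect of a larger supply on the 70% rule in section 5.4.** Take a patient seen at day 84 after receiving 98 loratadine tablets.

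- 59 to 68 tablets taken is 59/84 = 70.2% to 68/84 = 81.0% of those due, which passes.
- The same numbers are 59/98 = 60.2% to 68/98 = 69.4% of those dispensed, which fails.
- For famotidine, 118 to 137 tablets are 70.2% to 81.5% of 168 due, but 60.2% to 69.9% of 196 dispensed.

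If more tablets are dispensed, the denominator must be tablets due by the EGD date.

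**The case against.** The strongest reply is that this is a legitimate fixed-course design. Treatment is 12 weeks, the endpoint is defined after that course, and section 6.4 calls the histology a post-treatment examination. That stands: this is a loose window and not a contradiction. The nominal 14 weeks of participation in section 3.1 (2 weeks of DSQ plus 12 of drug) also suggests that many EGDs are meant to fall near day 84, so 14 days is the extreme. But no section requires that booking.

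A second reply is that harm needs three things the documents do not show: the drugs work, eosinophils return within two weeks, and enough EGDs are late. This also stands, and it limits the point to a conditional bias. The only relapse timing given (section 1.1) is several weeks for symptoms after topical corticosteroids, a different outcome and drug class. The six-week washout in section 4.2 is longer than the worst gap.

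A third reply is that the plan accepts larger tolerances. A patient just above 70% compliance may miss 84 - 59 = 25 loratadine doses, and section 4.1 allows diagnostic biopsies up to six months old. That is fair as to scale. It does not remove a gap that falls immediately before the measurement and is cheap to close.

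A reader might infer more in three ways, none of which the documents support.

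- **Drug clearance means lost effect.** For famotidine, section 5.1 says "the elimination half-life is 2.5-3.5 hours", so it is largely gone within a day. That says nothing about how fast eosinophils return, and for loratadine only a duration of action above 24 hours is given.
- **A definite loss of power.** Any such figure would need an assumed loss of effect and an assumed share of late EGDs. The documents give neither.
- **A gap beyond 14 days.** The prose of section 6.4 windows the appointment, but the schedule table puts the EGD in the same weeks 14-16 column.

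**Conclusion.** The gap is real and follows from the plan as written: 0 to 14 days off drug at the primary biopsy for a fully adherent patient. This assumes that the EGD falls inside the scheduled window and that patients stop when the 84-day supply ends. Any resulting bias would act on the active arm only and toward no difference, so it would not create a false finding of efficacy. Its size is unknown, and it is zero if eosinophils do not rebound within two weeks. The change is worth making because the primary endpoint is exposed and the remedy is small, not because a loss has been shown.

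**What to change.** **First choice, with no extra tablets.** In section 6.4 and the schedule table, require that the EGD be booked, when dosing starts, for day 84 to 87. Add a CRF field for the last-dose date, completed at the EGD. This caps the gap at 3 days for a fully adherent patient and keeps the 12-week exposure. The cost is one field, two edits and a tighter booking window for the two designated endoscopists.

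**If the 14-week window must stay.** Dispense 98 loratadine and 196 famotidine tablets, or matching placebo, and instruct patients in both arms to dose until the EGD. Then:

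- Record the last-dose date as above.
- In section 5.4, compute the 70% rule against tablets due by the EGD date.
- Change the 12-week wording to 12 to 14 weeks in sections 3.4, 3.5 and 7.2. If 7.2 is left alone, the analysis time point will no longer match the endpoint.
- In section 3.1, tie the second DSQ period to weeks 10-12 of treatment.
- Make conforming edits to treatment duration and supply in the Study Summary, 1.2, 3.3, 5.2, 5.3, 5.6, 6.1, 6.4 and the schedule table.

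The cost is 14 and 28 more tablets per patient, and exposure that varies from 12 to 14 weeks. The DSQ may still end up to two weeks before the biopsy, as it can now, but both would be on drug.
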